10.5. Appendix 5: Study Conduct During a Natural Disaster

GUIDANCE ON STUDY CONDUCT DURING THE COVID-19 PANDEMIC

It is recognized that the Coronavirus Disease 2019 (COVID-19) pandemic may have an impact on the conduct of this clinical study due to, for example, isolation or quarantine of participants and study-site personnel; travel restrictions/limited access to public places, including hospitals; study-site personnel being unavailable, isolated, or reassigned to critical tasks.

The sponsor is providing options for study related participant management in the event of disruption to the conduct of the study. This guidance does not supersede any local or government requirements or the clinical judgement of the investigator to protect the health and well-being of participants and site staff. If, at any time, a participant's travel to the study site is considered to be dangerous, study participation may be interrupted, and study follow-up conducted. If it becomes necessary to discontinue participation in the study, the procedures outlined in the protocol for discontinuing study intervention will be followed.

If, as a result of the COVID-19 pandemic, scheduled visits cannot be conducted in person at the study site, they will be performed to the extent possible remotely/virtually or delayed until such time that on-site visits can be resumed. At each contact, participants will be interviewed to collect safety data. Key immunogenicity endpoint assessments should be performed if required and as feasible. Participants will also be questioned regarding general health status to fulfill any physical examination requirement.

Every effort should be made to adhere to protocol-specified assessments for participants on study intervention, including follow up. Modifications to protocol-required assessments may be permitted after consultation with the participant, investigator, and the sponsor. Missed assessments/visits will be captured in the clinical trial management system for protocol deviations. Discontinuations of study interventions and withdrawal from the study should be documented with the prefix "COVID-19-related" in the eCRF.

If a participant has tested positive for COVID-19, the investigator should contact the sponsor's responsible medical officer to discuss plans for administration of study intervention, performing study assessments, and follow-up. Modifications made to the study conduct as a result of the COVID-19 pandemic should be summarized in the clinical study report.

GUIDANCE SPECIFIC TO THIS PROTOCOL:

Screening and Randomization

Enrollment of new participants may continue based on the investigator's assessment of risks
versus benefits, depending on the situation at a particular site, and the ability to monitor
participant safety.

Site Visits

• When site visits are not possible due to local/national guidelines, sites should collect the assessments via telephone visits or home-based visits, if the participant allows. The actual visit date and the type of visit (ie, telephone or home-based visit) should be captured in the eCRF according to the eCRF completion guidelines. Procedures that cannot be performed during a home-based visit (eg, blood samples), should be excluded.

Vaccine Administration

• When planning for vaccination visits, local/national or institutional guidelines will be followed. The study vaccine must be administered by a blinded qualified individual at the study site. If this is not possible, a solution may be considered in consultation with the sponsor and taking into consideration participant safety.

Informed Consent Form

Consenting and re-consenting of participants for the measures taken (including also remote
consenting by phone or video consultation) will be performed as applicable and according to
local guidance for informed consent applicable during the COVID-19 pandemic. The process
is to be documented in the source documents.

Source Data Verification/Monitoring

• In case on-site monitoring visits are not be possible, the site monitor may contact the investigator to arrange monitoring visits and activities remotely (in accordance with site and local requirements). Additional on-site monitoring visits may be needed in the future to catch up on source data verification.

Site Audits

 During the COVID-19 pandemic and at the impacted sites, study site GCP audits with direct impact/engagement from the investigator and study site personnel would not be conducted in order to comply with national, local, and/or organizational social distancing restrictions. Additional quality assurance activities such as remote audits or focused review of study related documents may take place with limited impact/engagement if possible.

10.6. Appendix 6: Thrombotic Events to be Reported as Potential AESIs

At the time of protocol writing, the list of thrombotic events to be reported to the sponsor as potential AESIs is provided below. Further guidance may become available on thrombotic events of interest.

MedDRA PTs for large vessel thrombosis and embolism

Aortic embolus, aortic thrombosis, aseptic cavernous sinus thrombosis, brain stem embolism, brain stem thrombosis, carotid arterial embolus, carotid artery thrombosis, cavernous sinus thrombosis, cerebral artery thrombosis, cerebral venous sinus thrombosis, cerebral venous thrombosis, superior sagittal sinus thrombosis, transverse sinus thrombosis, mesenteric artery embolism, mesenteric artery thrombosis, mesenteric vein thrombosis, splenic artery thrombosis, splenic embolism, splenic thrombosis, thrombosis mesenteric vessel, visceral venous thrombosis, hepatic artery embolism, hepatic artery thrombosis, hepatic vein embolism, hepatic vein thrombosis, portal vein embolism, portal vein thrombosis, portosplenomesenteric venous thrombosis, splenic vein thrombosis, spontaneous heparin-induced thrombocytopenia syndrome, femoral artery embolism, iliac artery embolism, jugular vein embolism, jugular vein thrombosis, subclavian artery embolism, subclavian vein thrombosis, obstetrical pulmonary embolism, pulmonary artery thrombosis, pulmonary thrombosis, pulmonary venous thrombosis, renal artery thrombosis, renal embolism, renal vein embolism, renal vein thrombosis, brachiocephalic vein thrombosis, vena cava embolism, vena cava thrombosis, truncus coeliacus thrombosis

• MedDRA PTs for more common thrombotic events

Axillary vein thrombosis, deep vein thrombosis, pulmonary embolism, MedDRA PTs for acute myocardial infarction*, MedDRA PTs for stroke*

Source: Shimabukuro T. CDC COVID-19 Vaccine Task Force. Thrombosis with thrombocytopenia syndrome (TTS) following Janssen COVID-19 vaccine. Advisory Committee on Immunization Practices (ACIP). April 23, 2021. https://www.cdc.gov/vaccines/acip/meetings/slides-2021-04-23.html.

*Vaccine Adverse Event Reporting System (VAERS) Standard Operating Procedures for COVID-19 (as of 29 January 2021) https://www.cdc.gov/vaccinesafety/pdf/VAERS-v2-SOP.pdf

10.7. Appendix 7: Protocol Amendment History

The Protocol Amendment Summary of Changes Table for the current amendment is located directly before the Table of Contents (TOC).

Amendment 1 (23 September 2021)

Overall Rationale for the Amendment: Based on Health Authority feedback, neutralizing antibody responses (assessed in the virus neutralization assay-A2 [VNA-A2]) will be added as secondary endpoint to the study to support the conclusions drawn from the comparisons using pre-F ELISA data as the primary endpoint.

Section Number	Description of Change	Brief Rationale
and Name		
1.1 Synopsis 3 OBJECTIVES AND ENDPOINTS 8.1 Immunogenicity Assessments 9.4.3.2 Secondary and Exploratory Endpoint	Adding RSV neutralizing antibody responses (assessed in the virus neutralization assay-A2 [VNA-A2]) as secondary endpoint. Note: no change in volume of blood sampling required.	Following Health Authority feedback.
2.2 Background 11 REFERENCES	Experience with Ad26-vectored vaccines was added.	For alignment with the other supportive Phase 3 study protocols.
4.2.1 Study-Specific Ethical Design Considerations	The results of this study may be made available to all participants through a plain language summary at the conclusion of the study according to local standards/restrictions.	For alignment with the other supportive Phase 3 study protocols.
2.3.1 Risks Related to Study Participation 8.3.5 Pregnancy	In case of pregnancy, postnatal sequelae in the infant will not be followed-up. Note: Follow up info regarding the outcome of the pregnancy of the study participant themselves or of the partner of the participant will be requested (upon consent).	According to the current Janssen SOP 'Receipt, Follow-up, and Reporting of Janssen Medicinal Product Individual Case Safety Reports', follow-up of postnatal sequelae in the infant is not a requirement. The sponsor protocol template is planned to be modified to reflect this change.
8.3.1 Time Period and Frequency for Collecting AE, SAE, and AESI Information 8.3.6.1 Thrombosis with Thrombocytopenia Syndrome	The word 'symptomatic' was deleted from the definition of thrombocytopenia.	Definition of thrombocytopenia is broadened to include all cases of thrombocytopenia the investigators observe (including asymptomatic thrombocytopenia observed in participant's routine blood test or blood test performed concomitantly to any AE/SAE/hospitalization, or any other) in the period of 6 months after vaccination; these should be reported as potential TTS cases (please refer to Section 8.3.6).
Throughout the	Minor grammatical, formatting, or spelling changes	Minor errors were noted
protocol	were made.	

1. INTRODUCTION

This statistical analysis plan (SAP) contains information needed to perform the complete safety and immunogenicity analysis of the VAC18193RSV3003 trial. It applies to all the analyses described in Section 9.5 of the clinical trial protocol (CTP). The specifications of individual tables, listings and figures to be generated in each analysis will be described in a separate data presentation specifications (DPS) document.

1.1. Objectives and Endpoints

Refer to Section 3 of the CTP. The statistical hypotheses are described in Section 2 of this document.

1.2. Study Design

Refer to Section 4.1 of the CTP for details on the study design, and section 6.3 of the CTP for details on randomization and procedures for maintaining the blind.

2. STATISTICAL HYPOTHESES

To demonstrate the primary objectives, the following hypotheses will be tested sequentially:

Null Hypothesis 1:

Ad26/protein preF RSV vaccine lots representing the critical quality attributes around the intermediate shelf-life (Group 2) induces inferior geometric mean titers (GMTs) of the pre-F ELISA titers on Day 15, compared to Ad26/protein preF RSV vaccine lots representing the critical quality attributes near release (Group 1).

Alternative Hypothesis 1:

Ad26/protein preF RSV vaccine lots representing the critical quality attributes around the intermediate shelf-life (Group 2) induces non-inferior GMTs of the pre-F ELISA titers on Day 15, compared to Ad26/protein preF RSV vaccine lots representing the critical quality attributes near release (Group 1).

Non-inferiority will be shown if the lower limit of the 2-sided 95% confidence interval (CI) around the estimated geometric mean titer ratio (GMR) of the intermediate shelf-life lots versus the release lots (Group 2/Group 1) lies entirely above 0.67.

If non-inferiority is shown for the intermediate shelf-life lots then the following hypotheses will be tested:

Null Hypothesis 2:

Ad26/protein preF RSV vaccine lots representing the critical quality attributes near the presumed end of shelf-life (Group 3) induces inferior GMTs of the pre-F ELISA titers on Day 15, compared to Ad26/protein preF RSV vaccine lots representing the critical quality attributes near release (Group 1).

Alternative Hypothesis 2:

Ad26/protein preF RSV vaccine lots representing the critical quality attributes near the presumed end of shelf-life (Group 3) induces non-inferior GMTs of the pre-F ELISA titers on Day 15, compared to Ad26/protein preF RSV vaccine lots representing the critical quality attributes near release (Group 1).

Non-inferiority will be shown if the lower limit of the 2-sided 95% CI around the estimated GMR (end of shelf-life lots versus release lots [Group 3/Group 1]) lies entirely above 0.67.

3. SAMPLE SIZE DETERMINATION

Refer to Section 9.2 of the CTP.

4. POPULATIONS (ANALYSIS SETS) FOR ANALYSIS

For vaccine studies, study intervention assignment will follow the as treated principle.

Table 2: Description of Analysis Sets

Analysis Sets	Description	
All Screened	This analysis set includes all participants screened for the study, regardless if they were screen failures or they got enrolled in the study.	
	Rescreened participants are counted only once.	
Full Analysis Set (FAS)	The full analysis set (FAS) will include all participants who received study vaccine, regardless of the occurrence of protocol deviations.	
	All safety and participant information analyses will be based on the FAS.	
Per-protocol Immunogenicity (PPI) Set	The Per-protocol Immunogenicity (PPI) Set will include all randomized participants who received study vaccine, and for whom immunogenicity data are available. Samples taken after a participant experienced a major protocol deviation expected to impact the immunogenicity outcomes will be excluded from the PPI analysis.	
	The list of major protocol deviations that would lead to elimination from the immunogenicity analysis will be specified in the major protocol violation criteria document, which will be finalized before database lock and unblinding.	
	The primary analysis set for analyses related to RSV immunogenicity is the PPI Set. As a sensitivity analysis, key tables may also be based on the FAS.	

5. STATISTICAL ANALYSES

5.1. General Considerations

5.1.1. Study Phases

A baseline (or reference) value will be defined as the value of the last available assessment prior to vaccination on Day 1. If there was no immunogenicity assessment done pre-vaccination, the assessment post-vaccination on Day 1 can be used as the baseline value for the immunogenicity analysis, if available.

The results of the safety analysis will be presented by phase. Immunogenicity results will be presented per scheduled time point as appropriate. Listings will be shown per phase and time point.

Study day or relative day is defined as follows:

- Study Day = visit date date of Day 1 + 1; if visit date >= date of Day 1 (date of vaccination).
- Study Day = visit date date of Day 1; if visit date < date of Day 1 (date of vaccination).

5.1.2. Phase Definitions

The phases in the study will be constructed as follows:

Table 3: Phase Definitions

	Phase		Period	Interval		
Phase	#	Period	#	From	To	
Screening	1			Date and time of signing the informed consent form	One minute prior to start of post dose period	
Regimen	2	Post- dose	1	Date and time of vaccination	Minimum of: a) 23:59 at the date of last contact (for early discontinuation) b) 23:59 at the database cut-off date for analyses conducted before the final analysis. c) maximum of (28 days after vaccination at 23:59, scheduled visit 28 days after vaccination at 23:59)	
Follow-up	3			One minute after Post-dose period end.	Minimum of: a) 23:59 at the date of last contact (for early discontinuation or participants that completed the study) b) 23:59 at the database cut-off date for analyses conducted before the final analysis.	

The adverse events of special interest (AESI) analysis will be performed once by phase and once by time interval. The definition of the time intervals is shown in the table below. Additionally, in the tables a '0-56 days post-dose' interval and a '0-6 months post-dose' interval should also be shown. The '0-56 days post-dose' interval is the combination of the '0 - 28 days post-dose' interval and the '29 - 56 days post-dose' interval. The '0-6 months post-dose' interval is the combination of the '0 - 28 days post-dose', '29 - 56 days post-dose' and '57 days - 6 months post-dose' intervals.

Table 4: Definition of intervals

Dose	Interval	From	То
Post-vaccination	0 - 28 days post dose	Date and time of the vaccination	 Min of: 23:59 at date of last contact (for discontinuations) 23:59 at date of DB cut-off for interim analyses Maximum (Date of vaccination + 28 days at 23:59, date of scheduled visit 4 weeks after vaccination at 23:59)

CONFIDENTIAL - FOIA Exemptions Apply in U.S.

discontinuations/completions)
23:59 at date of DB cut-off for interim

analyses

Interval Dose From To 29 - 56 days post One minute after the end Min of: of the interval 0-28 days dose 23:59 at date of last contact (for post dose discontinuations) 23:59 at date of DB cut-off for interim analyses Date of vaccination + 56 days at 23:59 57 days - 6 months One minute after the end Min of: of the interval 29 - 56 post-dose 23:59 at date of last contact (for

days post dose

Table 4: Definition of intervals

5.1.3. Visit Windows

For the immunogenicity analysis, assessments will be allocated to an analysis visit based on the planned visit as captured in the CRF. Visits that are out of the protocol-defined visit windows (see Table 5 below) will not be included in the per-protocol immunogenicity analysis. However, they may be included in sensitivity analyses.

Table 5: Visit Windows for Immunogenicity Analysis

Analysis time point label	Target day	Window of target day	
(Relative to Day 1)	(Relative to Day 1)	(days)	
Day 1	1	(-∞, 1]	
Day 15	15	[12, 22]	
Day 183	183	[169, 197]	

5.2. Participant Dispositions

Participant information will be shown for the full analysis set.

The number of participants in the following disposition categories will be summarized throughout the study by intervention group and overall:

- participants screened
- participants in the FAS
- participants vaccinated and not randomized
- participants randomized and not vaccinated
- participants not randomized and not vaccinated
- participants randomized and vaccinated
- participants who discontinued study
- reasons for termination

Also, the number of participants and percentage per phase will be tabulated.

Other participant information variables: demographics and baseline characteristics, major protocol deviations, and concomitant medications will be analyzed as described in Appendix 2, Appendix 3 and Appendix 4, respectively. Medical history and concomitant diseases will be tabulated.

5.3. Primary Endpoint(s) Analysis

5.3.1. Definition of Endpoint(s)

The primary endpoint is the pre-F enzyme-linked immunosorbent assay (ELISA) antibody titers at 14 days after vaccination.

5.3.2. Analysis Methods

The primary immunogenicity objective will be assessed by calculating the 2-sided 95% CIs for the difference in log₂-transformed Day 15 pre-F ELISA titers for each of the comparisons (i.e., Group 2 versus Group 1, and Group 3 versus Group 1).

The CIs will be calculated via an analysis of variance (ANOVA) including all groups (i.e., Groups 1 to 3) with the log₂-transformed Day 15 pre-F ELISA titers as dependent variable and group as independent variable. The CIs around the difference will be back-transformed to CIs around a GMR (GMT_{Group x}/GMT_{Group 1}, where x is 2 or 3) and compared to the non-inferiority margin of 0.67 (2/3).

Non-inferiority of Group 2 versus Group 1 is demonstrated if the 2-sided 95% CI for the GMR (GMT_{Group 2}/GMT_{Group 1}) of the Day 15 pre-F ELISA titers lies entirely above 0.67. If non-inferiority of Group 2 versus Group 1 is not demonstrated, the study fails. If non-inferiority of Group 2 versus Group 1 is demonstrated, then non-inferiority of Group 3 versus Group 1 can be tested: similarly, non-inferiority of Group 3 versus Group 1 is demonstrated if the 2-sided 95% CI for the GMR (GMT_{Group 3}/GMT_{Group 1}) of the Day 15 pre-F ELISA titers lies entirely above 0.67.

As a sensitivity analysis to assess the impact of baseline titers, the primary endpoint will also be evaluated adjusting for the respective baseline titers. In a second sensitivity analysis, different variances between the study groups will be allowed. Therefore, the CIs will be calculated via Welch's ANOVA.

The significance level (α) is 5% (2-sided). As the 2 primary objectives are tested sequentially and as no interim analyses before the primary analysis are planned, no multiplicity adjustments are needed.

The population for analyses related RSV immunogenicity is the PPI set. The choice of population for the different analyses are described in Section 4.

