The PPI Set will include all randomized participants who received study vaccine and for whom immunogenicity data are available. Samples taken after a participant experiences a major protocol deviation expected to impact the immunogenicity outcomes will be excluded from the PPI analysis.

The list of major protocol deviations that would lead to elimination from the immunogenicity analysis will be specified in the statistical analysis plan (SAP) or major protocol violation criteria document, which will be finalized before database lock and unblinding.

The primary analysis set for analyses related to RSV immunogenicity is the PPI Set. As a sensitivity analysis, key tables may also be based on the FA Set.

Immunogenicity Analyses

The primary immunogenicity objective will be assessed by calculating the 2-sided 95% CIs for the difference in log-transformed Day 15 pre-F ELISA titers for each of the comparisons (ie, Group 2 versus Group 1, and Group 3 versus Group 1).

The CIs will be calculated via an analysis of variance (ANOVA) including all groups (ie, Groups 1 to 3) with the log-transformed Day 15 pre-F ELISA titers as dependent variable and group as independent variable. The CIs around the difference will be back-transformed (by exponentiation) to CIs around a GMR $(GMT_{Group\ x}/GMT_{Group\ 1})$ where x is 2 or 3) and compared to the non-inferiority margin of 0.67 (2/3).

Non-inferiority of Group 2 versus Group 1 is demonstrated if the 2-sided 95% CI for the GMR (GMT_{Group 2}/GMT_{Group 1}) of the Day 15 pre-F ELISA titers lies entirely above 0.67. If non-inferiority of Group 2 versus Group 1 is not demonstrated, the study fails. If non-inferiority of Group 2 versus Group 1 is demonstrated, then non-inferiority of Group 3 versus Group 1 can be tested: similarly, non-inferiority of Group 3 versus Group 1 is demonstrated if the 2-sided 95% CI for the GMR (GMT_{Group 3}/GMT_{Group 1}) of the Day 15 pre-F ELISA titers lies entirely above 0.67.

As a sensitivity analysis to assess the impact of baseline titers, the primary endpoint will also be evaluated adjusting for the respective baseline titers. For immunogenicity, baseline is considered as the last assessment pre-vaccination. In a second sensitivity analysis, different variances between the study groups will be allowed. Therefore, the CIs will be calculated via Welch's ANOVA.

No formal statistical testing of the secondary and exploratory immunogenicity endpoints is planned.

[figure not shown]

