4. STUDY DESIGN

4.1. Overall Design

This is a randomized, double-blind, multicenter, interventional Phase 3 study in adult participants aged \geq 60 to \leq 75 years. A target of 750 participants will be randomized in parallel in a 1:1:1 ratio to 1 of 3 groups (see Table 2).

All participants will receive Ad26/protein preF RSV vaccine on Day 1 by the IM route.

Table 2: Study Design

Group	N	Vaccination on Day 1
1	250	Ad26.RSV.preF 1.0×10 ¹¹ vp + RSV preF protein 150 μg (representing critical quality attributes around release)
2	250	Ad26.RSV.preF 2.5×10 ¹⁰ vp + RSV preF protein 150 μg (representing critical quality attributes around the intermediate shelf-life)
3	250	Ad26.RSV.preF 1.0×10 ¹⁰ vp + RSV preF protein 150 μg (representing critical quality attributes near the end of shelf-life)

N = number of participants; vp = viral particles

After vaccination, participants will remain under observation at the study site for at least 15 minutes for presence of any acute reactions and solicited events. Any unsolicited AEs, solicited local (injection site) or systemic AEs, and vital signs (systolic and diastolic blood pressure [sitting], heart rate, respiratory rate, and body temperature) will be documented by study-site personnel following this observation period. In addition, participants will record solicited signs and symptoms in a participant diary beginning in the evening of the day of vaccination and on a daily basis for 7 days post-vaccination (Section 8).

The reporting periods of AEs, SAEs, and AESIs are detailed in Section 8.3. The reporting periods for concomitant therapy are outlined in Section 6.8.

Blood will be collected from all participants pre-vaccination and at 14 days and 6 months post-vaccination to assess humoral immune responses.

Safety issues that might arise from this study may be escalated to an independent DMC, as needed.

The study comprises a screening period (Day -28 to Day 1), vaccination for each participant on Day 1, and a 6-month safety and immunogenicity follow-up period. The end of the study is defined as the last participant's last visit.

Over the entire study, the total blood volume to be collected from each participant will be approximately 30 mL.

Unscheduled study visits may be performed based on investigator's clinical judgment and may include further evaluations, as needed.

A diagram of the study design is provided in Section 1.2 (Figure 1). Further details are provided in the Schedule of Activities.

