9.2. Sample Size Determination

Sample size calculations are performed under the following assumptions:

• a 10% decrease in GMT of the groups with aged lots (Group 2 and Group 3) versus the group with the non-aged lot (Group 1) (ie, assuming a true GMR of Day 15 pre-F ELISA titers equal to 0.9)

- a standard deviation of 1.3 at the log₂ scale for pre-F ELISA on Day 15^a
- a non-inferiority margin of 0.67 (2/3)
- a 2-sided α of 5%
- hierarchical testing (ie, first Group 2 versus Group 1; if non-inferiority is demonstrated, then Group 3 versus Group 1)

A total of 236 evaluable participants per group are needed to have 95% power to demonstrate non-inferiority for each comparison separately. With this sample size, the overall power to demonstrate non-inferiority of Group 3 versus Group 1 as the second comparison in the hierarchy is at least 90%.

To account for exclusions from the Per-protocol Immunogenicity (PPI) Set (see Section 9.3 for the definitions of the analysis sets), dropouts, and missing samples, approximately 250 participants per group should be enrolled.

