9.4.3. Immunogenicity Analyses

9.4.3.1. Primary Endpoints

The primary immunogenicity objective will be assessed by calculating the 2-sided 95% CIs for the difference in log-transformed Day 15 pre-F ELISA titers for each of the comparisons (ie, Group 2 versus Group 1, and Group 3 versus Group 1).

The CIs will be calculated via an analysis of variance (ANOVA) including all groups (ie, Groups 1 to 3) with the log-transformed Day 15 pre-F ELISA titers as dependent variable and group as independent variable. The CIs around the difference will be back-transformed (by exponentiation) to CIs around a GMR ($GMT_{Group\ x}/GMT_{Group\ 1}$ where x is 2 or 3) and compared to the non-inferiority margin of 0.67 (2/3).

Non-inferiority of Group 2 versus Group 1 is demonstrated if the 2-sided 95% CI for the GMR (GMT_{Group 2}/ GMT_{Group 1}) of the Day 15 pre-F ELISA titers lies entirely above 0.67. If non-inferiority of Group 2 versus Group 1 is not demonstrated, the study fails. If non-inferiority of Group 2 versus Group 1 is demonstrated, then non-inferiority of Group 3 versus Group 1 can be tested: similarly, non-inferiority of Group 3 versus Group 1 is demonstrated if the 2-sided 95% CI for the GMR (GMT_{Group 3}/GMT_{Group 1}) of the Day 15 pre-F ELISA titers lies entirely above 0.67.

As a sensitivity analysis to assess the impact of baseline titers, the primary endpoint will also be evaluated adjusting for the respective baseline titers. For immunogenicity, baseline is considered as the last assessment pre-vaccination. In a second sensitivity analysis, different variances between the study groups will be allowed. Therefore, the CIs will be calculated via Welch's ANOVA.

The pre-F ELISA titers will be summarized descriptively. For continuous parameters, descriptive statistics of the actual values (geometric mean and 95% CI) will be calculated at all timepoints. Additionally, geometric mean fold increases from baseline and corresponding 95% CIs will be

calculated. Graphical representations of immunogenicity parameters will be created as applicable. For categorical variables, frequency tables will be presented.

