5.3.3. Handling of Missing and/or Unquantifiable Immune Response Data

Missing immune response data will not be imputed.

Values below the lower limit of quantification (LLOQ) will be imputed based on the type of analysis:

- Values below LLOQ will be imputed to LLOQ/2, except for the calculation of the geometric mean of the increase from baseline where values below LLOQ will be imputed to LLOQ.
- Values above the upper limit of quantification (ULOQ) will be imputed with the ULOQ.

The ULOQ and LLOQ values per assay will be available in the database.

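### Adjusting the deciding non-inferiority model for baseline pre-F titer would narrow both confidence intervals at no cost in participants or samples, unless baseline and Day 15 titers are almost uncorrelated

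*SAP*

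**What the plan says.** The deciding CIs for Group 2/Group 1 and Group 3/Group 1 come from one ANOVA "with the log-transformed Day 15 pre-F ELISA titers as dependent variable and group as independent variable" (Protocol 1.1; the same model is in Protocol 9.4.3.1 and SAP 5.3.2). If Group 2 misses the 2/3 margin, the study has failed and Group 3 is not tested.

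The baseline-adjusted model is planned without a decision role: "As a sensitivity analysis to assess the impact of baseline titers, the primary endpoint will also be evaluated adjusting for the respective baseline titers" (SAP 5.3.2). The covariate's scale is not given.

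The data for it are already scheduled: "Blood will be collected from all participants pre-vaccination and at 14 days and 6 months post-vaccination to assess humoral immune responses" (Protocol 4.1).

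On power, Protocol 9.2 states: "A total of 236 evaluable participants per group are needed to have 95% power to demonstrate non-inferiority for each comparison separately". It adds at least 90% for Group 3 as second in the hierarchy. The SD of 1.3 is described as that of the Day 15 titer itself in one group of an earlier study, with no mention of baseline adjustment.

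Two rules bear on using baseline as a covariate. The protocol says "For immunogenicity, baseline is considered as the last assessment pre-vaccination" (9.4.3.1), whereas SAP 5.1.1 adds that, if no pre-vaccination assessment was done, "the assessment post-vaccination on Day 1 can be used as the baseline value for the immunogenicity analysis, if available". SAP 5.3.3 says "Missing immune response data will not be imputed".

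**The concern.** Two valid, prespecified models are available, and the documents give no reason for letting the less precise one decide. Because the tests are sequential, the width of the Group 2 interval governs the chance of reaching either conclusion.

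The plan meets its targets under its own assumptions. What is at stake is reserve if the evaluable fraction, the SD or the true GMR turns out worse than assumed. The gain is precision only: the unadjusted CI already allows for chance baseline imbalance, and type I error is controlled under both models.

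**Working it through.** **Inputs from Protocol 9.2.** Two-sided alpha 5%; margin 2/3; true GMR 0.9 for both aged groups; SD 1.3 on the log2 scale; n = 236 evaluable of about 250 per group. The correlation r between log2 baseline and log2 Day 15 titer is not in the documents. It is an assumption, shown as a range.

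**Reproducing the plan.**
- Distance from assumed truth to margin: log2(0.9) − log2(2/3) = −0.152 + 0.585 = 0.433.
- SE of a group difference: 1.3 × √(2/236) = 0.1197.
- The noncentral-t calculation gives 236 per group for 95% power (235 by normal approximation). Reading the margin as exactly 0.67 gives 244, so the plan used 2/3.
- With the three-group error term (df = 3 × 236 − 3 = 705), power is 95.1% per comparison.
- Power for both comparisons, simulated with the shared Group 1, is 91.4%. The lower bound is 2 × 0.951 − 1 = 90.2%. Both agree with the stated minimum of 90%.
- CI half-width: 1.963 × 0.1197 = 0.235 log2 units, a factor of 2^0.235 = 1.177. The smallest observed GMR that passes is (2/3) × 1.177 = 0.785.

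**Adjusted model.** Residual SD = 1.3 × √(1 − r²); df = 704; the variance of the difference is multiplied by 1 + 1/703 for expected chance imbalance in baseline. Equivalent n = 236/(1 − r²), which ignores that last factor.

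| r | CI width vs unadjusted | Power, each | Power, both | Smallest passing GMR | Equivalent n per group |
|---|---|---|---|---|---|
| unadjusted | 1 | 95.1% | 91.4% | 0.785 | 236 |
| 0 | 1.001 | 95.1% | 91.3% | 0.785 | 236 |
| 0.1 | 0.996 | 95.2% | 91.6% | 0.784 | 238 |
| 0.2 | 0.980 | 95.8% | 92.5% | 0.782 | 246 |
| 0.3 | 0.955 | 96.6% | 93.9% | 0.779 | 259 |
| 0.5 | 0.867 | 98.6% | 97.5% | 0.768 | 315 |

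Simulated trials analysed both ways gave mean width ratios of 1.001, 0.955 and 0.867 at r = 0, 0.3 and 0.5.

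**Break-even.** With complete baselines, adjustment narrows the expected CI once |r| exceeds about 0.04. If participants without a baseline were dropped, break-even rises to about 0.11, 0.15 and 0.23 for 1%, 2% and 5% missing (assumed rates).

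**Type I error.** In 20,000 simulated trials per case at a true GMR of 2/3 (r = 0.2, 0.3, 0.5), one-sided error was 2.4–2.5% for both models. With 2% of baselines missing and filled with the overall mean, ANCOVA error was 2.4–2.6% and power per comparison 95.7%, 96.6% and 98.7%.

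**If a planning assumption is missed** (each scenario is assumed; power for both comparisons):

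| Scenario | Unadjusted | r = 0.2 | r = 0.3 | r = 0.5 |
|---|---|---|---|---|
| 225 of 250 evaluable (10% loss; the plan allows 14/250 = 5.6%) | 89.8% | 91.1% | 92.7% | 96.8% |
| SD 1.4 | 86.1% | 87.6% | 89.6% | 94.9% |
| GMR 0.85 in both aged groups | 73.3% | 75.3% | 77.9% | 86.6% |

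**The case against.** The strongest reply is that nothing is broken. The ANOVA is valid, consistently stated and powered as claimed, and the adjusted result will be reported anyway. The benefit depends on an r that the documents do not supply. At 0.1 or 0.2 it is only about 0.2 or 1.1 points of power for both comparisons, and it becomes material only from about 0.3. The loss scenario that falls below 90% is assumed and misses by 0.2 points; at 230 evaluable (8% loss) the unadjusted plan still gives about 90.6%.

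All of that stands, and it limits the point to a recommendation. It does not favour the unadjusted model as the one that decides: with complete or filled baselines the loss at r = 0 is under 0.1% of CI width. As written, a favourable adjusted result also cannot change a failed primary test.

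The practical objections are fair but answerable.
- **Approval:** Protocol 10.3.1 requires a formal amendment and prior ethics committee approval, so this is more than an edit.
- **Secondary GMRs:** those for VNA A2 follow the primary method and need a stated covariate. They are descriptive, so this carries no error-rate consequence.
- **Welch's ANOVA:** it relaxes equal variances only in the group-only model. It can stay as a sensitivity analysis in that role.
- **Baseline rules:** the current primary analysis needs no baseline definition or covariate imputation, whereas the new one does. The planned sensitivity analysis already needs the two baseline definitions reconciled.

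**Conclusion.** The point holds as an efficiency improvement, not a correction. Under the plan's assumptions, adjustment raises power for both comparisons from 91.4% to between 91.6% (r = 0.1) and 97.5% (r = 0.5), the precision of about 238 to 315 participants per group in place of 236. With no correlation the cost is negligible. Confidence in the direction is high; confidence in the size is only moderate, because r is assumed. The sponsor could estimate r from the earlier study that supplied the SD, if baseline titers are available there, before committing. The conclusion also assumes that missing baselines do not remove participants from the model.

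**What to change.** Before unblinding, in the synopsis, Protocol 9.4.3.1 and SAP 5.3.2:

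1. Make the primary model an ANCOVA of log2 Day 15 pre-F ELISA titer with group and log2 baseline pre-F ELISA titer as terms. Keep the 2/3 margin and the fixed sequence.
2. Retain the group-only ANOVA, and Welch's ANOVA, as sensitivity analyses.
3. Use one baseline definition in both documents: that of SAP 5.1.1, including its Day 1 fallback, with the protocol sentence aligned to it. Baselines below LLOQ follow the existing LLOQ/2 rule.
4. In SAP 5.3.3, add an exception limited to the covariate: a baseline still missing is set to the overall mean log2 baseline across groups. Outcomes stay unimputed, so no participant is lost from the primary analysis.
5. State that the descriptive VNA A2 GMRs use the same model with the baseline VNA A2 titer.

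The cost is a protocol amendment with its approvals, a SAP update and one degree of freedom out of 705. No extra samples, assays or participants are needed, and the adjusted analysis is already planned.
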